2. LIST OF ABBREVIATIONS

ADR Adverse Drug Reaction

AE Adverse Event

AESI Adverse Event of Special Interest

AKI Acute Kidney Injury

ALT Alanine Aminotransferase
AST Aspartate Aminotransferase

BI Boehringer Ingelheim
BMI Body Mass Index
CA Competent Authority
CDA Confidentiality Agreement

CI Confidence Interval
CKD Chronic Kidney Disease
CRF Case Report Form

CRO Contract Research Organization

CV Cardiovascular

DKA Diabetic Ketoacidosis
DM Diabetes Mellitus
DMP Data Management Plan

EC Ethics Committee

eCRF Electronic Case Report Form

eGFR Estimated Glomerular Filtration Rate

ENCePP European Network of Centres for Pharmacoepidemiology and

Pharmacovigilance

EU European Union

FDA Food and Drug Administration

GPP Good Pharmacoepidemiology Practice
GVP Good Pharmacovigilance Practices

HbA1c Glycated Hemoglobin

IEC Independent Ethics Committee
INR International Normalized Ratio
IRB Institutional Review Board

ISF Investigator Site File

KA Ketoacidosis

KDIGO Kidney Disease: Improving Global Outcomes

KIMS Korea Index of Medical Specialties
KPAC Korean Pharmaceutical Affairs Code

KPBMA Korea Pharmaceutical and Bio-Pharma Manufacturers Association

KRPIA Korean Research-based Pharma Industry Association

LPVM Local Pharmacovigilance Manager MAH Marketing Authorisation Holder

MedDRA Medical Dictionary for Regulatory Activities

ONIS New Data Collection Protocol

Page 6 of 54

Study number: 1245-0323 Document number: c42645766-03

Proprietary confidential information © 2024 Boehringer Ingelheim International GmbH or one or more of its affiliated companies

MFDS Ministry of Food and Drug Safety

ONIS Observational and Non-Interventional Study

PASS Post-Authorisation Safety Study

PMP Project Management Plan
PMS Post Marketing Surveillance

QV Qualification Visit

RMP Risk Management Plan SAE Serious Adverse Event SAP Statistical Analysis Plan

SFQ Site Feasibility Questionnaire
SGLT-2 Sodium Glucose Cotransporter 2
SOP Standard Operating Procedure
UACR Urine Albumin-Creatinine Ratio

ONIS New Data Collection Protocol

Page 7 of 54

Study number: 1245-0323 Document number: c42645766-03

Proprietary confidential information © 2024 Boehringer Ingelheim International GmbH or one or more of its affiliated companies

3. RESPONSIBLE PARTIES

An ONIS lead who is appointed by coordinating all required activities, in order to:

- manage the study in accordance with applicable regulations and internal standard operating procedures (SOPs),
- direct the study team in the preparation, conduct, and reporting of the study,
- order the materials as needed for the study,
- ensure appropriate training and information of a Contract Research Organization (CRO) and site staff.

delegate study tasks such as monitoring activities, data management, statistical analysis, etc. to a CRO and the delegated tasks are performed in accordance with the applicable SOPs of CRO or BI as described in a Project Management Plan (PMP).

Participating study sites are general hospitals or clinics. Contact details and the list of all investigators are kept in a stand-alone document.

4. ABSTRACT

Name of company:			
Boehringer Ingelheim			
Name of finished medicinal product: JARDIANCE®			
Name of active ingredient: SGLT-2 inhibitor (A10BK03) / Empagliflozin			
Protocol date:	Study number:	Version/Revision:	Version/Revision date:
26 July 2023	1245-0323	3.0	28 February 2024
		-interventional study to monito pagliflozin 10 mg) in Korean pa	
Rationale and background:	This Post Marketing Surveillance (PMS) is a local Post Authorized Safety Study (PASS) stipulated in the local PMS regulation: A surveillance that the Marketing Authorization Holder (MAH) conducts during the re-examination period (4-6 years) in order to collect, review, confirm, or verify the information regarding the safety and efficacy of commercially licensed new drugs requiring the re-exmination. This real world data is submitted to the Ministry of Food and Drug Safety (MFDS) and the surveillance results are reflected in the approved information. JARDIANCE® was submitted for Chronic Kidney Disease (CKD) indication to MFDS and a mandatory post-approval study was requested to collect safety		

ONIS New Data Collection Protocol

Document number: c42645766-03

Page 8 of 54

Study number: 1245-0323 Proprietary confidential information © 2024 Boehringer Ingelheim International GmbH or one or more of its affiliated companies

	data from 250 participants in a single arm study conducted in a real world environment for 2 years, which is now accepted to meet the Risk Management Plan (RMP) regulation.			
	Although the safety profile of JARDIANCE® has been established in clinical trials, it is possible that patients with more diverse conditions than those enrolled in clinical trials will be treated with JARDIANCE® in routine clinical setting. Therefore, this PMS can provide supplementary data to monitor the safety of JARDIANCE® in Korean patients with CKD in a real-life clinical setting.			
Research question and objectives:	The primary and secondary objectives are to monitor the safety and efficacy of JARDIANCE® in Korean patients with CKD in routine clinical practice.			
Study design:	Single-arm, open-label, multi-centre, observational and non-interventional study based on newly collected data			
Population:	Inclusion criteria:			
-	 Age ≥ 19 years at enrolment 			
	Patients diagnosed with CKD			
	 Patients with CKD starting JARDIANCE[®] for the first time in accordance with the approved label in Korea 			
	Patients who have provided informed consent and signed the data release consent form			
	Exclusion criteria:			
	 Patients with previous exposure to JARDIANCE® 			
	 Patients with hypersensitivity to empagliflozin or to any of the excipients 			
	Patients with type 1 diabetes			
	Patients with history of diabetic ketoacidosis (DKA)			
	 Patients with rare hereditary conditions of galactose intolerance, 			
	the Lapp lactase deficiency or glucose-galactose malabsorption			
	 Patients who are pregnant or are breastfeeding or who plan to become pregnant during the study period 			
Variables:	Outcomes of safety:			
	All reported adverse events (AEs) in participants who take at least one dose of JARDIANCE®			
	Outcomes of efficacy:			
	Change in Urine Albumin-Creatinine Ratio (UACR) from baseline to 12 weeks and/or 24 weeks of treatment			
Data sources:	Participants' medical records			
Study size:	250 participants			
Data analysis:	All statistical analyses will be explorative in nature. Participant			
	characteristics will be reported using measures of central tendency (e.g., mean, median) and variance (standard deviation, quartiles) for continuous variables and using frequencies and percentages for count data. Frequency			

ONIS New Data Collection Protocol

Page 9 of 54

Study number: 1245-0323 Document number: c42645766-03

Proprietary confidential information © 2024 Boehringer Ingelheim International GmbH or one or more of its affiliated companies

	of safety events will be reported using frequencies and incidence with 95% confidence interval (CI). The changes of the efficacy outcomes from baseline will be compared in an exploratory sense via paired t-test.	
Milestones:	Start of data collection: March 2024	
	End of data collection: November 2025	
	Interim report 1: January 2024	
	Interim report 2: January 2025	
	Final study report: February 2026	

5. AMENDMENTS AND UPDATES

Number	Date	Section of study protocol	Amendment or update	Reason
1	06 October 2023	9.3.2.1 Primary outcomes	· Added liver injury and lower limb amputation as AESI.	According to the review comment of MFDS
			· Added a description of specific adverse events (Severe hypoglycaemia, Urinary tract infection, Genital infection, Bone fracture, Urinary tract malignancy, Volume depletion, Acute kidney injury, Gout, Hyperkalaemia).	
2	06 October 2023	11.1 Deffinitions of adverse events	 Added definitions of liver injury and lower limb amputation. Added a description of specific adverse events. 	According to the review comment of MFDS
3	28 February 2024	Title page	Added EU PAS register number.	Add EU PAS register number
4	28 February 2024	4. Abstract	Changed the study period and sample size.Changed the milestones.	Reflection of MFDS approval

ONIS New Data Collection Protocol

Page 10 of 54

Study number: 1245-0323 Document number: c42645766-03

Proprietary confidential information © 2024 Boehringer Ingelheim International GmbH or one or more of its affiliated companies

Number	Date	Section of study protocol	Amendment or update	Reason
5	28 February 2024	6. Milestones	Changed the milestones.	Reflection of MFDS approval
6	28 February 2024	7. Rationale and background	Changed the study period and sample size	Reflection of MFDS approval
7	28 February 2024	9.1 Study design	Changed the safety data collection period	According to the change in the study period
8	28 February 2024	9.2.2 Study population	Changed the sample size	Due to change in the study period
9	28 February 2024	9.2.2.3 Exclusion critera	Deleted "patients on dialysis".	According to local label revision
10	28 February 2024	9.2.3 Study visits	Added "serum creatinine" to laboratory tests.	To collect serum creatinine levels
11	28 February 2024	9.5 Study size	Changed the study period and sample size.	Reflection of MFDS approval
12	28 February 2024	9.7.1 Analysis sets	Changed the sample size.	Due to change in the study period
13	28 February 2024	11.1 Deffinitions of adverse events	Added definitions of specific AEs.	To clarify the definitions of specific AEs
14	28 February 2024	11.2 Adverse event and serious adverse event collection and reporting	Added a description of study discontinuation of pregnant participants.	To clarify study discontinuation for pregnant participants

ONIS New Data Collection Protocol

Page 11 of 54

Study number: 1245-0323 Document number: c42645766-03

6. MILESTONES

Milestone	Planned Date
IRB/IEC approval	FEB 2024
Start of data collection	MAR 2024
End of data collection	NOV 2025
Interim report 1	JAN 2024
Interim report 2	JAN 2025
Registration in the EU PAS register	OCT 2023
Final report of study results:	FEB 2026

7. RATIONALE AND BACKGROUND

CKD is defined as abnormalities of kidney structure or function, present for >3 months, with implications for health.[P22-08628] CKD is a major public health problem worldwide and also strongly interrelated with other major disease, including Diabetes and Cardiovascular (CV) disease, which remain the leading causes of morbidity and premature death in this patient population.[R13-0282]

CKD is a major, growing, health concern in Asia and the substantial burden of CKD in Asia may be prevalent at similar or even greater magnitudes as compared with those observed in other parts of the world including North America and Europe.[R22-3432]

Empagliflozin is an orally available, potent, and selective inhibitor of the renal dependent sodium glucose cotransporter 2 (SGLT-2). Its selective inhibition reduces renal reabsorption of sodium and glucose. This leads to both increased urinary sodium and glucose excretion.[c37800399-01] While urinary sodium excretion returns to normal within few days of empagliflozin administration, the effect on urinary glucose continues for as long as the medication is used.[c37800399-01] Empagliflozin also reduces blood pressure, arterial stiffness and measures of myocardial workload, likely through various proposed mechanisms, and improves other potential CV risk factors.[P15-00589, P15-09541]

The EMPA-KIDNEY trial showed that treatment with empagliflozin significantly reduced the risk of kidney disease progression or CV death by 28% compared with placebo. Treatment with empagliflozin demonstrated clinically meaningful cardio-renal benefits in a broad range of CKD patients. Empagliflozin was also superior to placebo in reducing the risk of hospitalisations for any cause by 14% and treatment effects were consistent regardless of diabetes status, estimated Glomerular Filtration Rate (eGFR) or albuminuria levels.

ONIS New Data Collection Protocol

Page 12 of 54

Document number: c42645766-03 Study number: 1245-0323

Proprietary confidential information © 2024 Boehringer Ingelheim International GmbH or one or more of its affiliated companies

The frequencies of prespecified non-serious AE, AEs leading to treatment discontinuation, and SAEs were similar to placebo. The results from the AEs and safety laboratory analyses were generally consistent with the known safety profile of empagliflozin. [c37800399-01]

This PMS is a local PASS stipulated in the local PMS regulation: A surveillance that the MAH conducts during the re-examination period (4-6 years) in order to collect, review, confirm, or verify the information regarding the safety and efficacy of commercially licensed new drugs requiring the re-examination. This real world data is submitted to MFDS and the surveillance results are reflected in the approved information.

During the review of the CKD indication MFDS imposed this mandatory post-approval commitment to submit safety data of 250 participants under real world conditions for 2 years, which is now accepted to meet the RMP regulation.

Although the safety profile of JARDIANCE[®] has been established in clinical trials, it is possible that patients with more diverse conditions than those in clinical trials will be enrolled in routine settings. Therefore, this PMS can provide supplementary data to monitor the safety of JARDIANCE in Korean patients with CKD in a real-life situation.

ONIS New Data Collection Protocol

Page 13 of 54

Study number: 1245-0323 Document number: c42645766-03

Proprietary confidential information © 2024 Boehringer Ingelheim International GmbH or one or more of its affiliated companies

8. RESEARCH QUESTION AND OBJECTIVES

8.1 PRIMARY OBJECTIVE

The primary objective is to monitor the safety profile of JARDIANCE® in Korean patient with CKD in routine clinical practice.

8.2 SECONDARY OBJECTIVE

The secondary objective is to monitor the efficacy of JARDIANCE® by evaluating changes in UACR after 12 and/or 24 weeks of treatment.

9. RESEARCH METHODS

9.1 STUDY DESIGN

This is a single-arm, open-label, multi-centre ONIS based on newly collected data. As per local regulations, safety data will be collected for about 2 years.

This study will be carried out by enrolling patients in a consecutive manner into the study requiring completion of case report forms (CRFs) for all participants who initially administered JARDIANCE® following the study start date until the planned number of participants is reached. Prior to the initiation of the study, written contract shall be concluded, and this contract shall be concluded among (CRO (if applicable) and with the head of the site or the investigator with his/her consent.

Participants will be managed according to local practice guidelines. The choice of treatment will be solely at the discretion of the investigator. JARDIANCE® will be administered according to the approved label in Korea. Hence there are no additional risks to participants by participating in this ONIS.

9.2 SETTING

9.2.1 Study sites

Approximately 20 sites with approximately 20 or more investigators will participate in the study. To minimize selection bias at the site level, the goal is to have participating centers reflect a balance between general hospitals and clinics. The investigators will be mainly internists or nephrologists.

As provided in the Standards for Re-examination of New Drugs, etc. of MFDS Notification, should select study sites according to the following requirements:

ONIS New Data Collection Protocol

Document number: c42645766-03

Page 14 of 54

Study number: 1245-0323 Proprietary confidential information © 2024 Boehringer Ingelheim International GmbH or one or more of its affiliated companies

Equipment/facility and personel support capable of fully achieving the goal of investigation should be available.

- The investigators should have specialized knowledge of the drug subject to investigation and the indication, have completed education/training necessary for performing the investigation, or have practical experience.
- Study site and the investigators should strictly keep confidential the record of personal data of patients/participants.
- The investigators should be fully aware of the Standards for Re-examination of New Drugs, etc.] and study protocol.

9.2.1.1 Managing Site and Physician/Investigator Selection, Contracting and Training See Annex 3.

9.2.2 Study population

250 participants will be enrolled. To minimize the selection bias, consecutive participants from each site who meet inclusion criteria will be enrolled in this study.

9.2.2.1 Main diagnosis for study entry

Patients diagnosed with CKD in Korea

When diagnosing CKD, the criteria of Kidney Disease: Improving Global Outcomes (KDIGO) can be referred to (Annex 6).

9.2.2.2 Inclusion criteria

- Age ≥ 19 years at enrolment
- Patients diagnosed with CKD
- Patients with CKD starting JARDIANCE® for the first time in accordance with the approved label in Korea
- Patients who have provided informed consent and signed the data release consent form

9.2.2.3 Exclusion criteria

- Patients with previous exposure to JARDIANCE®
- Patients with hypersensitivity to empagliflozin or to any of the excipients
- Patients with type 1 diabetes

ONIS New Data Collection Protocol

Study number: 1245-0323

Document number: c42645766-03

Page 15 of 54

Proprietary confidential information © 2024 Boehringer Ingelheim International GmbH or one or more of its affiliated companies

- Patients with history of Diabetic Ketoacidosis (DKA)
- Patients with rare hereditary conditions of galactose intolerance, the Lapp lactase deficiency or glucose-galactose malabsorption
- Patients who are pregnant or are breastfeeding or who plan to become pregnant during the study period

9.2.2.4 Investigation for participants of special interest

The participants who have signed the data release consent form, participants of special interest (geriatric (older than 65 years), pregnant women, hepatic impairment and other special population) among the participants who conducted investigation for safety assessment after the administration of JARDIANCE® can be further summarized into subgroups collected from this.

9.2.3 Study visits

9.2.3.1 Visit 1 (Baseline)

At Visit 1, the informed consent is obtained from the participant using the data release consent form. After obtaining written informed consent, the following data will be collected from the participant's medical record:

- Visit date
- Date of data release consent
- Diagnosis date of CKD
- Inclusion/exclusion criteria eligibility
- Demographics (age (month and year of birth), gender, current pregnancy status (female only), current breastfeeding status (female only), smoking status, alcohol intake status, history of type 2 Diabetes Mellitus (DM)
- Medical history (within 6 months)
- Past or concomitant medication use (within 1 month)
- Physical examination information (height, weight, Body Mass Index (BMI), blood pressure)
- Efficacy assessment: UACR (The measurement taken on the date closest to the visit date is collected. A value from up to 6 months prior to the visit date can be used as a baseline.)
- Other laboratory test results (Glycated Hemoglobin (HbA1c), eGFR, serum creatinine, etc.: if available)
- JARDIANCE[®] administration status (dose, frequency, total daily dose, start and end date)

ONIS New Data Collection Protocol

Page 16 of 54

Study number: 1245-0323 Document number: c42645766-03

Proprietary confidential information © 2024 Boehringer Ingelheim International GmbH or one or more of its affiliated companies

At Visit 1, the participant will be requested to contact the investigator in the event of any AEs noted after initiating JARDIANCE® treatment.

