9.2.3.2 Visit 2 (Follow-up 1: 12 weeks from Visit 1)

After 12 weeks from Visit 1, the participant returns for follow-up. The following data will be collected:

- Visit date
- Physical examination information (weight, BMI, blood pressure)
- Concomitant medication use
- Any changes in the JARDIANCE administration status
- Efficacy assessment: UACR (The measurement taken on the date closest to the visit date is collected.)
- Any changes in the laboratory test results (HbA1c, eGFR, serum creatinine, etc.: if available) if there is any lab result which was clinically significant compared to data before JARDIANCE® treatment
- Safety assessment: any AEs noted
- Study completion status (if applicable)
- Investigator's overall efficacy assessment (if applicable)

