9.2.4 Study discontinuation

BI reserves the right to discontinue the study overall or at a particular study site at any time for the following reasons:

- 1. Failure to meet expected enrolment goals overall or at a particular study site
- 2. Emergence of any effectiveness / safety information that could significantly affect continuation of the study, or any other administrative reasons
- 3. Violation of Good Pharmacoepidemiology Practice (GPP), the study protocol, or the contract by a study site, investigator or research collaborator, disturbing the appropriate conduct of the study

The investigator / the study site / research collaborator will be reimbursed for reasonable expenses incurred in case of study / site termination (except in case of the third reason).

Flow Chart 9.2.5

Data points	Baseline	Follow-up 1	Follow-up 2
Visit	1	2	3
Week	0	12	24
Data release consent	X		
Diagnosis	Χ		
Inclusion/Exclusion criteria	Χ		
Demographics (initial, gender,	Χ		
age, smoking status, alcohol			
intake status, history of type 2			
DM)			
Medical history ¹⁾	Χ		
Physical examination (blood	Χ	Х	X
pressure, height ²⁾ , weight, BMI)			
Past ³⁾ or concomitant therapies	Х		
JARDIANCE® administration status	Χ	Х	Х
UACR ⁴⁾	Х	Х	Х
Investigator's overall efficacy		X ^A	Х
assessment			
Other laboratory tests ⁵⁾	X ^B	X ^B	X ^B
AEs		X	Х
Study completion		X ^A	X

A: If applicable

B: If available

¹⁾ Medical history 6 months prior to Visit 1 is collected.

²⁾ Height is measured only in Visit 1.

³⁾ Past medications 1 month prior to Visit 1 are collected.

⁴⁾ Data performed on the date closest to each visit date are collected.

ONIS New Data Collection Protocol

Study number: 1245-0323 Document number: c42645766-03

Page 18 of 54

Proprietary confidential information © 2024 Boehringer Ingelheim International GmbH or one or more of its affiliated companies

5) Data performed on the date closest to each visit date can be collected. Laboratory test results such as eGRF, HbA1c, etc. are collected, if available.

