9.3.2.2 Secondary outcomes

The secondary outcome is the efficacy outcome as follows:

Change in UACR from baseline after 12 weeks and/or 24 weeks of treatment

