9.7.1.3 Number of participants for safety assessment

These include those who signed the data release consent form to participate in this study, took JARDIANCE® once at least, and were followed up by the investigator once or more. Reflecting the MFDS guideline, the cases below shall be excluded from safety analysis (defined below) set in the following order:

- a. Participants who did not signed (signature missing), or participants who signed on the data release consent form of JARDIANCE® CKD PMS prior to the contract date
- b. Participants who took JARDIANCE® prior to the contract date
- c. Participants who took JARDIANCE prior to signing the data release consent form
- d. Participants who have not taken JARDIANCE®
- e. Follow-up failure: Participants whose safety information cannot be obtained due to lost-to-follow-up
- f. Participants who were prescribed Jardiance for indications outside the local label

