9.7.1.4 Number of participants for efficacy assessment

These cases include those who signed the data release consent form to participate in this study, had at least one follow-up visit, took Jardiance*, and had at least some follow-up data for the efficacy.

Reflecting the MFDS guideline, the cases below shall be excluded from efficacy analysis (defined below) set in the following order:

a. Participants excluded from the safety analysis set listed in section 9.7.1.3.

ONIS New Data Collection Protocol

Page 22 of 54

Study number: 1245-0323 **Document number: c42645766-03**

Proprietary confidential information © 2024 Boehringer Ingelheim International GmbH or one or more of its affiliated companies

b. Participants with missing information of efficacy assessment listed in section 9.3.2.2.

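### The UACR collection rule takes the value nearest in time to each visit, in either direction, so a post-dose value can become baseline and a pre-dose value can become the week-12 result

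*Protocol*

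**What the plan says.** Protocol Section 9.2.3.1 (Visit 1) asks for the UACR nearest to the visit and adds: "A value from up to 6 months prior to the visit date can be used as a baseline". Sections 9.2.3.2 and 9.2.3.3 (Visits 2 and 3) use the same selection rule without any time limit: "The measurement taken on the date closest to the visit date is collected". Footnote 4 to the flow chart in Section 9.2.5 repeats it for every visit: "Data performed on the date closest to each visit date are collected".

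These values feed the only secondary outcome, in Section 9.3.2.2: "Change in UACR from baseline after 12 weeks and/or 24 weeks of treatment". They also determine the shift in albuminuria category in Section 9.3.2.3. Section 9.7.3 compares change from baseline by an exploratory paired t-test. Section 9.7.1.4 admits to the efficacy set participants who, among other conditions, "had at least some follow-up data for the efficacy", and removes those whose efficacy information is missing.

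On the timing of first intake, Section 9.7.1.3 excludes from the safety set, and Section 9.7.1.4 therefore from the efficacy set: "Participants who took JARDIANCE prior to signing the data release consent form". Consent is obtained at Visit 1.

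**The concern.** A nearest-date rule has no direction. The look-back sentence at baseline is a permission to use an older value; it does not bar a later one. Analysed participants start treatment at or after consent at Visit 1, so a sample shortly after Visit 1 may already be on treatment, and the rule can still select it as baseline. At follow-up the rule has neither a lower limit at first intake nor a window, so it can reach back to a pre-treatment sample.

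The secondary outcome is a change after a stated time on treatment. A pair in which both members are the same pre-dose sample says nothing about that, yet it enters the analysis as a change of zero. Read literally, the rule also leaves almost nothing missing, because any single UACR is the nearest one to every visit. The exclusion for missing efficacy information in Section 9.7.1.4 would then rarely operate.

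**Working it through.** The plan gives no figure to reproduce: Section 9.5 sets 250 participants from prevalence and market conditions, without an effect size or standard deviation. The check applies the written rule to example dates and then sizes the attenuation under stated assumptions.

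**Inputs.** Visits at days 0, 84 and 168 (weeks 0, 12 and 24 of the flow chart). First intake is taken as day 0, an assumption consistent with Section 9.7.1.3. The sample dates are illustrative, since the protocol gives no UACR testing frequency.

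**Rule.** For each visit, choose the sample with the smallest absolute distance in days.

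| Samples available (day) | Baseline | Week 12 | Week 24 | Consequence |
|---|---|---|---|---|
| −30, +7, +84, +168 | +7 | +84 | +168 | Post-dose baseline chosen (7 days away against 30), although a pre-dose value exists |
| −7, +180 | −7 | −7 | +180 | Baseline reused at week 12 (91 days away against 96); change exactly 0 |
| −7 only | −7 | −7 | −7 | One pre-dose value fills all visits; two changes of exactly 0 |
| −150, +20 | +20 | +20 | +20 | One post-dose value fills all visits |
| −14, +126 | −14 | +126 | +126 | One value serves both follow-ups (42 days from each) |

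In weeks, the second pattern is as simple as UACRs at weeks 0 and 26: they lie 12 and 14 weeks from week 12, so week 0 is selected.

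**Size.** Let f be the share of pairs showing no change, and suppose the true fall is 25%. Both are assumptions. Averaging on the log scale, the reported fall is 1 − exp[(1 − f) × ln 0.75], with ln 0.75 = −0.2877:

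- f = 10%: 1 − exp(−0.2589) = 22.8%
- f = 20%: 1 − exp(−0.2301) = 20.6%
- f = 30%: 1 − exp(−0.2014) = 18.2%

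The protocol does not state a scale for the change. If percentage changes are averaged directly, 25% × (1 − f) gives 22.5%, 20.0% and 17.5%.

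Zero change is exact for a reused value. It is the extreme case for a post-dose baseline, because an early sample may carry only part of the effect. If it carried half (again an assumption), the formula becomes 1 − exp[(1 − 0.5f) × ln 0.75], giving 23.9% at f = 10% and 21.7% at f = 30%.

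**After a fix.** With illustrative windows of days 42–125 and 126–210 (not protocol figures), a baseline limited to day 0 or earlier, and no reuse, the first pattern takes day −30 as baseline. The second has week 12 missing. The third has both follow-ups missing. In the fifth, day 126 counts once, at week 24.

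**The case against.** The best defence is that the intent is clear. The visit is called baseline, its data are taken from the medical record at Visit 1, its only stated window runs backward, and the outcome is worded as change after weeks of treatment. A sensible site would enter a pre-dose value first and post-dose values later, and a week-0 sample is not follow-up data in any ordinary sense. Visit windows and reuse rules are commonly left to the statistical analysis plan, which is not shown here, and Section 9.7 defers full detail to it.

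The intent is granted; the operating rule does not enforce it. Nor is this purely an analysis matter, because the rule decides which value is collected. If one nearest value per visit is entered, an analysis window defined later can reject it but may be unable to recover a better-timed one without a return to source records.

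Some stronger readings are tempting and do not hold. A reader might infer that a baseline up to six months old, set against a one-month medication history, hides any drug started in between. A drug still in use within the month before Visit 1 is captured, and later concomitant use is collected at Visits 2 and 3, so that inference fails for ongoing drugs. A reader might also fault the absence of an on-treatment restriction. JARDIANCE start and end dates and changes in administration are collected, so treatment status can be derived, and whether to restrict is an analysis choice. Nor is it right that the plan has no windows at all, since baseline has its look-back.

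**Conclusion.** The point stands as a defect in a stated collection rule. As written, it can select a post-dose baseline, a pre-dose week-12 value with zero change, or one sample for two visits, and this conflicts with the outcome in Section 9.3.2.2. The first two errors pull the estimated change toward zero. The third makes the two follow-up results the same measurement.

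The size is unknown. The range 22.8% to 18.2% for a true 25% fall rests on an assumed effect and on an assumed 10% to 30% of pairs showing no change; neither comes from the protocol.

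This should be fixed, but it does not threaten the study. It affects an exploratory secondary outcome and the albuminuria category shift. The primary safety outcomes do not use these values. A reader might infer that the rule could manufacture a benefit; these two errors act in the opposite direction.

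**What to change.** In Sections 9.2.3.1 to 9.2.3.3 and flow chart footnote 4, replace the nearest-date rule with the following:

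- Baseline is the last UACR on or before first intake and within 6 months before Visit 1.
- The week-12 and week-24 values must be sampled after first intake and within pre-stated, non-overlapping windows around each time point. The sponsor should choose the cut-points.
- Each measurement is used for one visit only.
- A visit with no qualifying measurement is missing.
- The UACR sample date is entered in the eCRF, with an edit check against the first-intake date.

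The cost is a few sentences of protocol text and some eCRF checks, with no added visits or tests. The downside is that some participants lose a week-12 or week-24 value, but only one that was not valid for that visit.
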